4.4. Subject Withdrawal Procedure

Subjects who discontinue the study early will complete an Early Termination visit 28 days (+/- 3 days) and complete a final safety follow-up phone call 60 days (+3 Days) after the last infusion. If a subject is randomized but not dosed with IP before Early Termination on Day 0, an Early Termination visit is not required.

Note: At the Early Termination visit, PFTs and MFTs must be conducted. MRIs do not have to be repeated if the last one was performed within 4 weeks of this visit.

4.5. Replacement of Study Subjects

All randomized subjects will be included in the study. Subjects who discontinued the study early will not be replaced.

4.6. Study Termination

FibroGen reserves the right to close any investigational site(s) or terminate the study at any time for any reason. Reasons for the closure of the study site or termination of a study by FibroGen may include (but are not limited to):

- Successful completion of the study at the investigational site
- The required number of subjects for the study has been recruited
- Failure of the Investigator to comply with the protocol, GCP guidelines or local requirements
- Safety concerns
- Inadequate recruitment of subjects by the Investigator

5. TREATMENT OF SUBJECTS

5.1. Study Treatment

5.1.1. Pamrevlumab or Placebo

Pamrevlumab is a fully human IgG1 kappa monoclonal antibody that binds to CTGF and is formulated as solution for administration by IV infusion. Peripheral or central venous access may be utilized at the discretion of the investigator.

Matching placebo is formulated as solution to be administered in a manner that is identical to pamrevlumab infusion.

5.1.1.1. Formulation

Pamrevlumab is supplied in single-use glass vials containing sterile, preservative-free solution (100 mg pamrevlumab/vial or 500 mg pamrevlumab/vial respectively). The solution is composed of 10 mg/mL pamrevlumab, 1.60 mg/mL L-histidine, 3.08 mg/mL L-histidine HCl, 8.01 mg/mL sodium chloride, and 0.05 mg/mL polysorbate 20, resulting in a solution with a tonicity of approximately 290 mmol/kg and a pH of 6.0.

The placebo formulation is of identical composition as the pamrevlumab formulation, except for the absence of pamrevlumab.

5.1.1.2. Study Drug Packaging and Labeling

Labels will be prepared and will comply with Good Manufacturing Practice requirements for labelling and local regulatory guidelines.

5.1.1.3. Study Drug Storage

Vials of pamrevlumab and placebo must be stored refrigerated (2°C to 8°C), in a temperature-controlled and monitored environment, protected from light, and in a securely locked area to which access is limited to appropriate study personnel. Documentation of the storage conditions must be maintained by the site for the entire period of study participation. Details regarding the reporting of temperature excursions can be found in the study IP Manual.

5.1.2. Study Drug Preparation

Pamrevlumab or placebo is infused undiluted after pooling the contents of the calculated number of vials in an empty infusion bag (total volume of fluid must not exceed 410 mL) according to the Dose Preparation Instructions in the Investigational Product (IP) Manual.

Pamrevlumab and placebo solutions for infusion must be stored refrigerated (2°C to 8°C) and administered within 48 hours of preparation or within 6 hours if left at room temperature after preparation. Pamrevlumab or placebo infusion solutions are administered by IV infusion (peripheral or central venous access), using an infusion set with a 0.2 µm in-line filter. Gravity infusion or use of an infusion pump are both acceptable methods of infusion as per local institutional standards.

5.1.3. Study Drug (Investigational Product) Administration

Dosing for pamrevlumab (or placebo) will be based on the weight obtained at screening and approximately every 12-weeks after Day 0. The total dose of pamrevlumab (or placebo) is not to exceed 4.1g. Subjects weighing more than 117 kg will receive the maximum allowable dose of 4.1g. The dose should be prepared in a volume of fluid that does not exceed 410 mL. IP will be administered as soon as possible after release from the site's pharmacy (or central pharmacy for sites in the United States utilizing home health care) and infused within 48 hours of preparation. IP will be administered by IV infusion, using an infusion set with a sterile, nonpyrogenic, low-protein-binding in-line filter (0.2-micron pore size). The dose, route, infusion rate and schedule for the administration of pamrevlumab or placebo is provided in Table 3.

Table 3: Pamrevlumab (or placebo): Dose, Route, and Administration

Agent	Dose	Route	Infusion Rate	Frequency
Pamrevlumab (or matching placebo)	35 mg/kg	IV	Not to exceed 150 cc/hour*	Every 2 weeks (+/- 3 days)

Note: DO NOT ADMINISTER STUDY DRUG AS AN IV PUSH OR BOLUS INJECTION, OR CONCURRENTLY IN THE IV LINE WITH OTHER AGENTS.

*Gravity infusion or use of an infusion pump are both acceptable methods of infusion as per local institutional standards.

Adjustments may be made to further slow the rate of infusion to less than 150 cc/hour in accordance with the investigator's clinical judgement.

The Investigator or a designee with proper medical training must be either present, or immediately available, during the first IP infusion and observation period (approximately 1 hour after the end of IP infusion) for each subject. If a subject has a significant infusion reaction, the infusion rate may be slowed or temporarily stopped, depending on the severity of symptoms. If a subject experiences a significant infusion reaction and continues Study Drug dosing, a physician should be immediately available during all subsequent infusions and observation periods at the site. Subjects who experience an infusion reaction will not be allowed to participate in Home Health Care (HHC). If the Investigator wishes to use premedication, (e.g., antihistamines, nonsteroidal anti-inflammatory drugs (NSAIDs)) for a subsequent infusion should be discussed with the sponsor Medical Monitor or designee. Infusions are to be continued until the total volume of the IP infusion has been administered. Subjects will remain at the study site for 1 hour after the end of the IP infusion for clinical observation for all study infusions.

Study Drug will be administered at a hospital or ambulatory setting with adequate facilities for managing medical emergencies. Medications for the treatment of acute reactions, including anaphylaxis, must be available to study site staff for immediate use. Medications for the treatment of acute reactions, including anaphylaxis, will be maintained at the subject's home for access by HHC nurse. There is no specific treatment for a pamrevlumab overdose or infusion reaction. Signs and symptoms should be managed with appropriate standard of care treatment.

The Sponsor may consider the use of properly trained home health care staff to administer the infusions of study drugs at the subject's home and corresponding study assessments during the

conduct of the study (after the completion of three infusions without safety concerns), consistent with institutional regulations and policies (see Section 5.1.4 for details).

The following procedures must be performed prior to each infusion:

- Vital signs (sitting blood pressure [BP], pulse, respiration, and temperature) within 30 minutes before starting the infusion
- Query subject and assess TEAEs
- Record concomitant medications

The following procedures must be performed after each infusion:

- Vital signs (sitting blood pressure [BP], pulse, respiration, and temperature) within 30 minutes after completion of the infusion
- Query subject and assess TEAEs

5.1.4. Home Health Care

The Sponsor may consider the use of properly trained home health care staff in specific regions/countries depending on local acceptance and adoption of home infusions to administer the infusions of study drugs at the subject's home and corresponding study assessments during the conduct of the study (after the completion of three infusions in study clinic without safety concerns), consistent with institutional regulations and policies. Home Health Care is optional and the decision to utilize is driven by a combination of the study site, the availability of qualified service, and Sponsor decision on overall feasibility. Subjects who experience an infusion reaction will not be allowed to participate in HHC. Following any adverse reaction at a HHC visit, the subject should speak to the study doctor and make a visit, if needed. The subject should also have his next scheduled infusion performed on site until the investigator deems it safe for the subject to return to home infusions. Medications for the treatment of acute reactions, including anaphylaxis are required to be present in the patient's home for all IMP administration visits. The pharmacy is required to dispense anaphylaxis medication for the first home visit, as the HCP will store it in a lockbox in the patient's home until the end of the study. HHC support will only be on weeks where other assessments are not being completed. PI maintains overall responsibility for patient care and their participation in the study. The HHC vendor requires PI signature on the PI Oversight Form, which outlines each GCP PI oversight responsibility and the supporting HHC vendor process. The Sponsor maintains oversight of the HHC vendor.

5.1.5. Missed Dose

Every attempt should be made to complete all study visits within window as outlined in the Schedule of Assessment (SOA) ([Appendix 1](#)).

Visit dates are scheduled based on the previous visits, not the baseline visit. Protocol-defined visits conducted outside the ± 3 day study visit window will be recorded as a protocol deviation. Missed doses are not to be made up through extra visits. If a subject misses more than two infusions in any 8-week period throughout the study, or two sequential infusions, the sponsor Medical Monitor should be notified. The reason for missed doses must be documented in the subject's clinical record.

Refer to the case report form (CRF) completion guidelines in the Study Reference Manual for additional information on CRF completion requirements for missed visits.

5.1.6. Study Drug Handling and Disposal

All IP provided by the Sponsor should be retained at the site until otherwise instructed in writing by the Sponsor (or designee). If local/regional/institutional policies do not allow the site to retain IP, the site must provide the sponsor (or designee) their drug destruction

SOP/process for review and approval. The Sponsor (or designee) will perform drug accountability and reconciliation for all study drug received at the site prior to approving study drug return/destruction. Upon completion of accountability/reconciliation or upon completion of the study or termination of the investigational site, all unused IP and all study drug that was not dispensed will be shipped to a destruction site designated by the Sponsor (or designee) for destruction. IV bags used to infuse study drug can be disposed of per institutional policy. Please refer to the IP Manual for additional information on study drug materials, management and accountability.

5.1.7. Treatment Compliance

All treatments are administered at the investigational site by qualified personnel and documented in the corresponding case report form (CRF).

5.2. Concomitant Medications

5.2.1. Permitted Concomitant Medications

Concomitant medications (any prescription and/or over-the-counter [OTC] preparation) and procedures or nondrug therapies (e.g., physical therapy, acupuncture, continuous positive airway pressure [CPAP]) used by a subject while participating in this clinical trial must be recorded from Screening Visit through the End-of-Study (EOS) Visit.

Other than the restrictions that follow, concomitant medications may be given at the discretion of the Investigator. It is expected that Investigators will provide optimal medical management of DMD and that subjects may be treated with concomitant medications for their various medical conditions. Optimal medical care must be provided, and Investigators should ensure, for example, that subjects maintain stable vital signs and laboratory test values during the course of the study.

Oral systemic corticosteroids or deflazacort are required, and must be recorded in the clinical chart and the CRF.

There are no safety concerns anticipated with the co-administration of pamrevlumab and COVID-19 vaccine. However, the Sponsor recommends a time separation between the administration of a COVID-19 vaccine and blinded study drug (pamrevlumab or placebo) of at least 48 hours to allow for better interpretation of any adverse events and their relationship to the vaccine or study drug. All adverse events should be reported to the sponsor per protocol.

The date of any vaccination administered from the time of screening until the end of the study must be reported in the Concomitant Medications CRF. COVID vaccinations should be captured in the Medical History section of EDC if administered prior to consent. COVID vaccinations while on study should be entered into the Concomitant Medication CRF.

5.2.2. Prohibited Concomitant Medications

Prohibited medications include any other (approved or investigational) agents for the treatment of DMD. The list of prohibited concomitant medications for treatment of DMD includes, but is not limited to, the following:

- eteplirsen (EXONDYS 51)
- ataluren
- golodirsen (VYONDYS 53)
- casimersen (AMONDYS 45)

Questions about concomitant medications should be discussed with the Sponsor Medical Monitor or designee. Patients who are on any approved therapy for DMD should not discontinue the therapy to be eligible for the study. However, if their approved therapy is discontinued for other reasons, they could be considered for participation in this study if they meet all eligibility criteria.

5.2.3. Contraception Requirements

A non-clinical study evaluating the potential effects of pamrevlumab on embryo-fetal development has been conducted (rabbit embryo-fetal development study 352021017). Preliminary results show pamrevlumab systemic exposure levels at 200 mg/kg to the pregnant female rabbits which resulted in fetal external and skeletal abnormalities are approximately 20-fold greater than the systemic exposure levels in humans at doses of 30mg/kg or 35 mg/kg in our current protocols.

No adverse effects of pamrevlumab administration were observed in a study of rat male and female fertility.

Therefore, male subjects who have partners with reproductive potential are required to use contraception during the conduct of the study and for 12 weeks after the last dose of study drug. Permitted contraceptive methods for the subjects include use of a condom (per Clinical Trial Facilitation Group (CTFG) recommendation version 1.1 21-09-2020, Section 2.3) or sexual abstinence during treatment and until the end of relevant systemic exposure in the partner of the woman of child bearing potential. Sexual abstinence is considered a highly effective method only if defined as refraining from heterosexual intercourse during the entire period of risk associated with the study treatments. The reliability of sexual abstinence needs to be evaluated in relation to the duration of the clinical trial and the preferred and usual lifestyle of the subject. The package insert regarding reproductive risks associated with the use of any corticosteroids used in this study should be evaluated and reviewed with the subject.

SWITZERLAND ONLY: Sexual abstinence is not considered an effective contraception method and local contraception regulatory guidelines must be followed accordingly.

6. ASSESSMENTS OF EFFICACY

6.1. Study Assessments

A signed and dated IRB/IEC-approved informed consent must be obtained before any study-specific assessments are performed. Assessments that are part of routine care are not considered study-specific and may be used at screening to determine eligibility. All subjects will be screened for eligibility before randomization. Only eligible subjects will be randomized into the study.

NOTE: In accordance with FDA/EMA Guidance: During the COVID-19 pandemic, the visit modality (e.g.: in-person versus remotely) and scheduling may be adjusted and conducted at the discretion of the Investigator, in accordance with the site's rules and recommendations, and using all necessary precautions. If a visit has to be done remotely, it can be conducted with any technology available to the site and study subjects, such as via tele-health visits, phone calls, etc.

6.1.1. Screening Period

All screening procedures must be performed within 28 days. Lead times for scheduling MRI may dictate timing of consenting subjects to maintain a 28 day window. Study procedures to be performed during the screening period can be found in the SOA. Subjects may have a specific procedure such as labs or PFTs repeated during screening to determine if the subject can enter the study. If the subject does not meet eligibility criteria, they must be screen failed. If the investigator feels that the assessments that resulted in screen failure did not adequately represent the subject's eligibility for the study, the subject may be re-screened at the discretion of the investigator. Repeating procedures within the screening window, or screen failing and rescreening a subject should be discussed with the medical monitor to evaluate which procedures should be repeated, which depends on the timing of rescreening.

Each subject's specific DMD genetic mutation should be entered in the EDC under medical history.

Due to the immunocompromised status of DMD patients, it is recommended the pneumococcal vaccine is administered as per national recommendations and standard of care for Duchenne Muscular Dystrophy patients on corticosteroids prior to study entry.

This vaccination recommendation can be met by administration of any applicable pneumococcal vaccine as per national guidance. This includes both conjugate (PCV13) and polysaccharide (PPSV23) vaccines. Patients must also agree to receive annual influenza vaccinations during the course of the study as needed.

6.1.2. Randomized Treatment Period

The study procedures and assessments are presented for the Randomized Treatment phase in [Appendix 1](#) and [Appendix 3](#) for the OLE.

The Randomized Treatment Phase begins on Day 0 (first infusion of IP) and continues through Week 52. Visit windows are within ± 3 days of the scheduled visit date (14 days from prior visit). Visit dates should be scheduled based on the previous visit, not the baseline visit.

Subjects who complete 52 weeks of treatment may be eligible to rollover into the OLE study where all subjects will be treated with pamrevlumab. If a subject discontinues the main study early for any reason, they will not be eligible for inclusion in the OLE.

6.1.3. End of Study/Safety Follow-up

All subjects enrolled will have an EOS/safety follow-up visit 28 days (\pm 3 Days) and a final safety follow-up phone call at 60 days (+3 days) after the last dose of study treatment. After the protocol-required reporting period (60 days (+ 3 Days) after the last dose), the investigator does not need to actively monitor subjects for SAEs. However, if the investigator becomes aware of an SAE/death that may be possibly related to study treatment after the protocol-required reporting period, the investigator may report the event to the Sponsor SAEs reported outside of the protocol-required reporting period will be captured within the safety database only as clinical trial cases for the purposes of expedited reporting.

6.1.4. Missed Visits

Visit dates are scheduled based on the previous visits, not the baseline visit. Protocol-defined visits conducted outside the \pm 3 day study visit window will be recorded as a protocol deviation unless there is an AE/SAE/intercurrent illness, in which case, study treatment may be withheld/interrupted, resulting in a “missed” visit. Refer to [Section 5.1.5](#) for additional details. For missed visits without an AE/SAE/intercurrent illness, the subject will be asked to resume the planned visit schedule and return for the next scheduled visit.

6.1.5. Unscheduled Visits

Unscheduled visits/assessments may be required at the discretion of the investigator. Unscheduled visit data will be captured accordingly in the clinical database.

Subjects who, in the judgment of the PFT or MFT technician or investigator, are unable to perform PFTs or MFTs adequately on a scheduled visit should repeat PFT or MFT assessment as soon as possible, or at minimum ensure to complete PFT or MFT assessment at the next scheduled on-site visit. If the subject is unable to perform PFTs or MFTs at week 52 then the subject must have an unscheduled visit at the nearest possible date to perform PFTs or MFTs.

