- f.) Full physical exam including chest auscultation
- g.) SAEs are collected from date of consent through EOS. AEs are collected from Day 0 through EOS. Number and percentage of bone fractures is captured from Day 0 through EOS. Bone fractures should be collected in the EDC as AEs, naming them using the specific guidelines in the electronic case report form completion guidelines.
- See [Section 7](#) for follow-up of AEs.
- h.) Concomitant medications and nondrug therapies must be reported beginning after informed consent is obtained and ending 60 days after the last treatment. Refer to [Section 5.2.2](#) for additional information on prohibited concomitant medications
- i.) HAHA, HAHA-NA and PK samples. See [Appendix 2](#) for PK, HAHA, and HAHA-NA sampling time points.
- j.) MFTs: Performance of Upper Limb (v. 2.0), and Hand Grip Test.
- k.) Local labs may be drawn prior to MRIs at the discretion of the investigator.
- l.) Vital signs (pulse, respiration, sitting BP, temperature) to be collected at every visit: within 30 minutes pre-infusion, and within 30 minutes after completion of infusion.
- m.) MFTs and PFTs are collected at screening and must be repeated prior to randomization and first infusion on Day 0. They may be conducted up to 3 days in advance of the Day 0 visit. The PFT results from both time points will be used to establish baseline values. The results from MFTs at Day 0 will be used to establish baseline.
- n.) Genetic Analysis samples will be collected in PAXgene tube; samples will be collected only from subjects who consent for this test. If subject consents to this optional sample, it may also be collected at an Unscheduled timepoint if it is not collected initially at Day 0.
- o.) Duchenne Video Assessment to be performed remotely within the interval between the prior scheduled study visit and next scheduled study visit.

- p.) If the subject is not going into the OLE, he should complete a final safety follow-up that consists of a visit at week 56 and a final safety follow-up phone call 60 days (+3 days) after the last infusion visit.
- q.) PFTs, MFTs, DVA and MRI only to be done at the early termination visit
- r.) Randomization may be performed within 2 days prior to Day 0 visit, after subject is confirmed eligible (see footnote “m”).

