#### **5.5. Analysis Visit Windows**

In accordance with FDA/EMA Guidance: During the COVID-19 pandemic, the visit modality (e.g.: in-person versus remotely) and scheduling may be adjusted and conducted at the discretion of the Investigator, in accordance with the site's rules and recommendations, and using all necessary precautions. If a visit must be done remotely, it can be conducted with any technology available to the site and study subjects, such as via tele-health visits, phone calls, etc.

Analysis visits, instead of the nominal visits from case report form (CRF), derived from visit dates and visit time windows will be used in the by-visit analyses. Unscheduled visits within a visit window (defined in [Appendix 2](#)) will be grouped into the closest scheduled visits based on the visit date. For subjects who have more than one measurement at a certain analysis visit, the measurement closest to the target date or the later assessment if there is a tie will be used, with the following exceptions:

- Liver function tests, such as Alanine Aminotransferase (ALT), Aspartate Aminotransferase (AST), Gamma-Glutamyl transferase (GGT), Alkaline Phosphatase (ALP), and total bilirubin, in which the maximum value will be used.
- Vital signs: the values on the infusion days will be used if applicable.
- Spirometry data: the Best Test Read (BTR) values will be used for analysis.

Efficacy parameters will be summarized by analysis visit defined by the following assessment windows ([Appendix 2](#)). The date of the first dose will be considered as the date of Day 1 for all analyses. Subjects will receive study drug every 2 weeks. The visit window for these visits is  $\pm 3$  days. Duchenne Video Assessment is to be performed in the subject's home up to 14 days prior to the scheduled study visit.

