#### 6.6.1.1.5. Population Summary for Treatment Comparison

Treatment difference of Least-square mean (LSMean) and SE at week 52 and corresponding 95% CI will be presented.

The random coefficient linear regression model (RCM), where within-patient errors follow a random coefficient regression model will be performed. The RCM model will include fixed effects of time, treatment, treatment-by-time interaction, with baseline ordinal PUL entry score as covariate. The time in the RCM model will be calculated as the elapsed weeks (considered as a continuous variable with 1 decimal place) from first dose date (or randomization date for subjects who drop out prior to any study medication) to the assessment date. All valid values including from unscheduled visits will be included.

The residual plot from the PROC MIXED output will be examined. If the residual plot shows a systematic pattern rather than a random scatter, then the linearity assumption may not be appropriate. In case of non-linearity, MMRM will be used as the primary analysis method, which is currently listed as one of the sensitivity analyses in next section.

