Were all tests valid?  
 (i.e., representative of child's true function)      Yes     No

If no, which tests were invalid?	And why?
Hand Held Myometry	 Testing Environment (i.e. equip. malfunction, fire alarm, disruption)  General health (i.e. stomachache, cold, flu)  Travel delays (i.e. lack of sleep; testing not performed at regular time)  Inappropriate clothing  Behavior  Musculoskeletal issue (i.e. injury, muscle cramping, tendinitis)  Other (please explain in comment section of worksheet)
PUL	 Testing Environment (i.e. equip. malfunction, fire alarm, disruption)  General health (i.e. stomachache, cold, flu)  Travel delays (i.e. lack of sleep; testing not performed at regular time)  Inappropriate clothing o  Behavior  Musculoskeletal issue (i.e. injury, muscle cramping, tendinitis)  Other (please explain in comment section of worksheet)

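### The SAP's closest-to-target rule ignores test adequacy, so by-visit PUL and grip analyses can keep an inadequate score and drop the repeat that the protocol asked for

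*Protocol*

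**What the plan says.** **Protocol.** Section 6.1.5 says that subjects who, in the technician's or investigator's judgement, "are unable to perform PFTs or MFTs adequately on a scheduled visit should repeat PFT or MFT assessment as soon as possible", or at minimum at the next on-site visit. For Week 52 it adds a stronger sentence: if the subject cannot perform the tests, "then the subject must have an unscheduled visit at the nearest possible date to perform PFTs or MFTs". The footnotes to Appendix 1 define the tests concerned: "MFTs: Performance of Upper Limb (v. 2.0), and Hand Grip Test".

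**SAP.** Section 5.5 groups unscheduled results with the nearest scheduled visit. Where one analysis visit holds several results, "the measurement closest to the target date or the later assessment if there is a tie will be used, with the following exceptions". The exceptions are liver tests (maximum value), vital signs (infusion-day value) and spirometry (best test read). MFTs are not among them.

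The PUL worksheet in SAP Appendix 3 asks "Were all tests valid", separately for hand-held myometry and PUL, and offers reasons such as illness, injury, behaviour and equipment failure. SAP 5.5 does not use the answer.

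For the primary random coefficient model (RCM), SAP 6.6.1.1.5 has a different data rule: "All valid values including from unscheduled visits will be included". Validity is graded for spirometry (Protocol 6.2.5) but not defined for MFTs.

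**The concern.** The repeat exists to supply a usable value when the first test was not a fair measurement. A selection rule that looks only at dates can undo this: it may keep the score that the evaluator rejected and drop its replacement.

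The rule matters wherever there is one value per subject per analysis visit:

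- the grip strength MMRM, step 4 of the testing sequence in SAP Table 1;
- the PUL MMRM, a sensitivity analysis that becomes primary if the residual plot contradicts linearity;
- the MI ANCOVA, jump-to-control and tipping-point analyses, all built on one PUL value at each of Weeks 16, 28, 40 and 52.

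Keeping poor scores adds noise. If they fall unevenly between arms of about 41, it also adds bias. In the RCM the risk is different: with validity undefined, the rejected test and its repeat could both enter.

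**Working it through.** **1. Do the original and its repeat share a window?** SAP Table 9 has MFT targets at days 113, 197, 281 and 365 (7 × week + 1). The first three windows end at days 155, 239 and 323, the midpoints between targets. So 155 − 113 = 239 − 197 = 323 − 281 = 42 days remain after target, and the Week 52 window stays open until the first OLE infusion or the end of the treatment period. A repeat within 14 days of an on-target visit is therefore in the same window at Weeks 16, 28 and 40. At Week 52 it is too, if done before that window closes.

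**2. Which result is kept?** Let the original fall *e* days from target and the repeat *g* days later. The original is kept if |e| < |e + g|; a tie goes to the later test.

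- e ≥ 0 and g ≥ 1: the original is always kept.
- e < 0: the repeat is kept only if the original was early by at least g/2 days.
- g = 0 (same-day repeat): a tie by date, so the repeat is kept.

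**3. How often, under an assumed drift?** Protocol 6.1.2 schedules each visit from the previous one, within ±3 days, so actual days can drift from target. I assume independent deviations, uniform on −3 to +3 days, summed over the 8 two-week steps to Week 16 or the 26 to Week 52. This is an assumption, not a figure in the documents. Exact probability that the inadequate test is kept:

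| Gap to repeat | Week 16 | Week 52 |
|---|---|---|
| 1 day | 53% | 52% |
| 3 days | 60% | 56% |
| 7 days | 73% | 63% |
| 14 days | 87% | 74% |

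With a single ±3-day deviation and no accumulation, the figures are 57%, 71%, 100% and 100%.

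**4. Plan's power figures.** With a difference of 2.0, SD 2.9 and a two-sided 0.05 t-test, 46 per arm gives 90.5% and 41 per arm gives 87.0%. Both agree with the plan (90% with 92 subjects; 87% with 82 in SAP section 7).

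**5. Illustrative effect on a by-visit PUL analysis.** Suppose a fraction *p* of Week 52 tests are inadequate, scored *d* points low and repeated on a later day, and a share *r* of them is kept. Then q = p × r and SD′ = √(2.9² + q(1 − q)d²). I take r = 0.56 to 0.74, the Week 52 values for gaps of 3 to 14 days.

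- *p* = 5%, *d* = 4, r = 0.56: q = 0.028, SD′ = √(8.41 + 0.44) = 2.97, power 85.3%.
- *p* = 5%, *d* = 4, r = 0.74: q = 0.037, SD′ = √(8.41 + 0.57) = 3.00, power 84.8%.
- Extreme case, *p* = 10%, *d* = 6: SD′ = 3.21 to 3.30, power 80% to 77%.

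Neither *p* nor *d* has a source in the documents. No planning SD is given for grip, so no power figure can be worked out for it.

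**The case against.** The strongest reply is that the primary analysis is not governed by this rule. The RCM uses actual elapsed weeks and takes valid values from unscheduled visits too, so it does not discard the repeat. This stands. A reader might infer that the primary PUL result rests on rejected tests, or that its power drops to 75%. The documents support neither. The RCM makes no closest-to-target choice, and 75% follows only if every inadequate test is kept (r = 1) in the extreme case of 10% of subjects reading 6 points low.

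Other points that stand:

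- It is tempting to say that the inadequate test always wins. It does not: a same-day repeat wins the tie, and a next-day repeat is close to a coin toss.
- The general duty to repeat is a recommendation. The Week 52 obligation is triggered by inability to perform the test, which may leave no competing score.
- SAP 6.6.1 allows only one missing item per domain. A PUL test with more gaps has no total, and the repeat is then used automatically. However, an item scored as unable counts as 0, so a poor test can still produce a total.
- Protocol 6.2.4 requires trained evaluators who have passed proficiency, the same evaluator per subject, and video QC at Week 52. Inadequate tests may be few.
- CRF completion rules are in a Study Reference Manual outside these documents. Scores judged inadequate may not be entered at all, and the worksheet answer may not reach the database.
- Selection by date is objective. Selection by judgement could let evaluators swap low scores for higher ones.

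These points limit the size of the problem. They do not remove it: followed as written, SAP 5.5 ignores adequacy for the two MFTs, although Protocol 6.1.5 sets the same repeat rule for spirometry and MFTs.

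**Conclusion.** The gap is real and modest. Where an inadequate PUL or grip test has a score and is repeated on a later day in the same window, SAP 5.5 keeps the inadequate score whenever the original was on or after target. Under the assumed drift at Week 52 this is roughly half to three quarters of cases.

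The only confirmatory test affected unconditionally is grip, which is tested formally only if steps 1 to 3 succeed. The PUL MMRM is confirmatory only if linearity fails; the MI-based analyses are checks on the primary result. For by-visit PUL analyses the illustrative loss is about 2 percentage points of power (87% to about 85%), on assumed values of 5% and 4 points. For the RCM the issue is narrower: the missing definition of a valid MFT could let both tests of a pair enter.

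The logic of the rule needs no assumption. The frequencies depend on the drift model, and the power figures on rates that the documents do not give.

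**What to change.** Add an MFT exception to SAP 5.5, for example: *a PUL or grip result that the blinded evaluator recorded at the visit as not adequately performed (the worksheet validity item) is superseded by its repeat done before the first OLE infusion; the original is used only if there is no repeat.* Refer to the same definition of valid in SAP 6.6.1.1.5, so that such a pair does not enter the RCM twice.

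The change costs a short SAP edit before database lock and a check that the worksheet answer is captured in the database. Its downside is that selection then depends on the evaluator's judgement. That judgement must be recorded at the visit, before any repeat and before unblinding. The present closest-to-target selection can be kept as a sensitivity analysis, to show whether replacing scores changes the result.
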